### **Reticular erythematous Ulcerative (REU) score**

The REU score was developed as a semi-quantitative scale, measuring disease severity based on 3 dimensions: reticulation, erythema and ulceration. Scores for each of the 3 clinical dimensions will add up to a total weighted score (REU score).

Summary statistics for the REU score will be provided for absolute and percentage change from baseline by visit up to end of study for each treatment group.

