**Table 1-1 Objectives and related endpoints.**

Objective(s)	Endpoint(s)
Primary objective(s)	Endpoint(s) for primary objective(s)

To demonstrate the clinical efficacy of secukinumab 300 mg every 4 weeks (Q4W) in subjects with cutaneous lichen planus (CLP), mucosal lichen planus (MLP), or lichen planopilaris (LPP) inadequately controlled by topical therapies, with respect to improvement in Investigator's Global Assessment (IGA) response by Week 16, compared to placebo.

	

Achievement of IGA response at Week 16 Patients diagnosed with biopsy-proven forms of CLP, MLP or LPP will be considered responders if they achieve an absolute IGA score ≤2 at Week 16

Secondary objective(s)	Endpoint(s) for secondary objective(s)

The secondary objectives of this trial comprise the following:

- evaluate the efficacy of secukinumab 300 mg Q4W compared to placebo throughout 16 weeks in Treatment Period 1;

- evaluate the long term efficacy of secukinumab 300 mg Q4W throughout 32 weeks in Treatment Period 2;

- evaluate the efficacy of secukinumab 300 mg Q2W in Treatment Period 2;

- evaluate the safety profile of secukinumab 300 mg throughout the duration of the study.

Detailed assessments are described the next section.

	
All subtypes	
Investigator's Global Assessment (IGA)	

Achievement of at least 2 points improvement from baseline in the IGA score at Week 16 and 32, and throughout the duration of the study

Achievement of IGA 0/1 score at Week 16 and 32, and throughout the duration of the study

Objective(s)	Endpoint(s)

• Dermatology Life Quality Index (DLQI)

	

• Absolute and relative change in DLQI from baseline to Week 16 and 32, and throughout the duration of the study

• Achievement of DLQI 0/1 score at Week 16 and 32, and throughout the duration of the study, among the subset of subjects with DLQI <math>\geq 2</math> at baseline

• Patient assessment of itch (NRS)

	

• Absolute and relative change in NRS from baseline to Week 16 and 32, and throughout the duration of the study

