## 2 Statistical methods

### 2.1 Data analysis general information

Novartis will be performing the analysis. Statistical software SAS version 9.4 or later will be used.

All data will be analyzed separately for each cohort (predominantly CLP, predominantly MLP, LPP), unless specified otherwise.

Summary statistics for continuous variables will include N, mean, standard deviation, minimum, lower quartile, median, upper quartile, maximum. Summary statistics for discrete variables will be presented in contingency tables and will include absolute and relative frequencies.

All listings will be presented by cohort and treatment groups.

Footnotes in the outputs will be kept to a minimum.

Footnotes will generally be provided for

- abbreviations used in the output; abbreviations used on several outputs, e.g. for listings in [\[Appendix 16.2\]](#) can be presented on a separate page and do not have to be repeated as footnotes on each listing
- sorting order of categories, e.g. for sorting within MedDRA (Medical Dictionary for Regulatory Activities) hierarchy levels
- MedDRA version used for reporting of MedDRA coded data

Footnotes will generally NOT be given for

- units displayed on the output
- interpretation of results (e.g. “odds ratio larger 1 favors active treatment”)
- information that can be retrieved from the statistical section of the clinical study report (CSR) unless it is not identifiable from the output, e.g.
  - explanation of analysis model used unless results of more than one model are displayed in an output
  - derivations of variables (e.g. BMI will not be explained in a footnote)
- information that will be provided in the clinical study protocol and/or methods section of the CSR (e.g. baseline definition if this is specified in the statistical section of the CSR)

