#### Investigator's Global Assessment (IGA)

The following IGA related endpoints are considered:

- **IGA  $\geq 2$  points improvement response:** defined as achieving an  $\geq 2$  IGA score decreasing compared with baseline (thus at least achieving an IGA score of  $\leq 2$ ).
- **IGA 0 or 1 response:** defined as achieving an IGA score of 0 or 1 (thus at least achieving an IGA  $\geq 2$  points improvement)

For IGA  $\geq 2$  points improvement response and IGA 0 or 1 response from Week 1 to Week 16, comparisons between the 300 mg Q4W treatment regimen and placebo groups will be conducted using the Fisher exact test. Estimates of the difference of response rates between the 300 mg Q4W treatment regimen and placebo groups together with 95% confidence intervals will be presented.

Summary statistics for IGA  $\geq 2$  points improvement and IGA 0 or 1 response by visit from baseline up to the end of study for each treatment group will be presented in contingency tables with the number and percentage of subjects in each category.

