#### **LPP Activity Index (LPPAI)**

LPPAI is a numeric score to quantify the signs and symptoms of LPP (Chiang, 2010). Subjects with an LPPAI reduction greater than 85% over pretreatment values were considered responders, with 25% to 85% reduction were considered partial responders, and with less than 25% reduction were considered non-responders.

Summary statistics will be provided for absolute and percentage change from baseline of LPPAI score by visit up to the end of study for each treatment group.

The number and proportion of LPPAI responders and partial responders will be presented by visit up to the end of study for each treatment group.

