**Table 2-5 Overview of analysis methods for secondary efficacy variables**

Variable(s)	Cohorts applied	Summary statistics for discrete data	Statistical analyses	Summary statistics for continuous data	Graphs*
IGA response over time a	CLP, MLP, LPP	X	Fisher exact test @ Week 1- 16		X
DLQI 0/1 response over time	CLP, MLP, LPP	X			X
DLQI total score and item score overtime	CLP, MLP, LPP			X	X b
Patient Assessment of Itch (NRS) over time (3 questions)	CLP, MLP, LPP			X	
Patient Assessment of Pain (NRS) over time (3 questions)	CLP, MLP, LPP			X	
PSAD over time	CLP	X			X c
REU over time	MLP			X	X d
OLPSSM over time	MLP			X	
LPPAI responder and partial responder over time	LPP	X			
LPPAI score over time	LPP			X	X d
Scalpdex over time	LPP			X	

\*Line plots. The graphs may only be presented in the Rshiny app where appropriate.

aIGA responses include: 1) IGA ≥2 points improvement response and 2) IGA= 0 or 1 response.

bTotal DLQI score change from baseline by cohort.

cPlotted as a categorical variable.

dTime course of percent change from baseline.

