## 2.6.2 Statistical hypothesis, model, and method of analysis

Not applicable

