## **2.11 Patient-reported outcomes**

[figure not shown]
Please refer to [Section 2.6](#) and [Section 2.13](#) for the analysis method of Patient-reported outcomes.

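### For REU and LPPAI, the readable SAP plans by-arm summaries only, although the Period 1 secondary objective is a comparison with placebo; a baseline-adjusted difference at Week 16 would be a cheap improvement

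*SAP*

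**What the plan says.** SAP Table 1-1 gives the first secondary objective as to "evaluate the efficacy of secukinumab 300 mg Q4W compared to placebo throughout 16 weeks in Treatment Period 1". Changes in REU (MLP cohort) and LPPAI (LPP cohort) from baseline to Week 16 are among the endpoints listed under the secondary objectives.

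SAP 2.6.1 then treats the endpoints in two ways:

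- **Binary.** For IGA improvement of at least 2 points and for IGA 0/1: "Estimates of the difference of response rates between the 300 mg Q4W treatment regimen and placebo groups together with 95% confidence intervals", plus Fisher's exact test. DLQI 0/1 also gets a between-arm difference with a 95% interval. The primary endpoint, IGA ≤2, has its own Bayesian difference with a credible interval (SAP 2.5.2).
- **REU and LPPAI scores.** For REU: "Summary statistics for the REU score will be provided for absolute and percentage change from baseline by visit". For LPPAI: "Summary statistics will be provided for absolute and percentage change from baseline of LPPAI score by visit". Both are given for each treatment group, with no difference, interval or model.

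SAP 2.6.2, the place for a secondary model, reads "Not applicable". In Table 2-5 the column for statistical analyses has one entry, "Fisher exact test @ Week 1- 16", on the IGA row. Protocol 12.5.1 likewise plans only summary statistics for the REU and LPPAI scores.

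**The concern.** The objective is comparative and the plan estimates effects against placebo for its secondary binary endpoints. The two disease-specific clinician scores have no prespecified contrast. Protocol 4.1 explains the cohort design by the use of subtype-specific assessments, and protocol 8.3.5 describes the IGA as a first attempt at a unified score. REU and LPPAI are therefore natural support for the primary result in their cohorts.

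With 24 and 12 patients per cohort, an unspecified contrast leaves several choices open after the data are seen: which visit, absolute or percentage change, crude or baseline-adjusted. No decision in the documents depends on these scores, so what is at stake is the quality of the supporting evidence.

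**Working it through.** **1. Is a contrast planned anywhere in the readable text?** The absence rests on the REU and LPPAI paragraphs of SAP 2.6.1. Table 2-5 and SAP 2.6.2 agree with it but do not prove it: Table 2-5 shows no analysis for DLQI 0/1, which does get a difference with interval in 2.6.1, and 2.6.2 is empty although Fisher tests are planned. The Table 2-5 line plots for REU and LPPAI are descriptive.

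**2. The plan's own figure.** Enumerating all outcomes of Binomial(24, 0.5) and Binomial(12, 0.2), with Beta(1/3, 1/3) priors and both proof-of-concept criteria, gives 0.7118. SAP Table 3-1 states 0.712. The sample-size statement stands and does not involve REU or LPPAI.

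**3. What a reader can already build.** SAP 2.1 provides the inputs: "Summary statistics for continuous variables will include N, mean, standard deviation, minimum, lower quartile, median, upper quartile, maximum". A crude Welch interval for the difference in mean change is ± t × √(s₁²/n₁ + s₀²/n₀).

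**4. What baseline adjustment adds.** The documents give no SD and no baseline-to-Week-16 correlation ρ. Results are therefore in SD units of the score, with ρ assumed and equal SDs. With 1/24 + 1/12 = 0.125 and N = 36:

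- change-score variance: 2(1 − ρ) × 0.125
- ANCOVA variance: (1 − ρ²) × 0.125 × (1 + 1/(N − 4)) = (1 − ρ²) × 0.125 × 1.03125

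| ρ | Change score | ANCOVA | Variance reduction |
|---|---|---|---|
| 0.3 | 0.175 | 0.117 | 33% |
| 0.5 | 0.125 | 0.097 | 23% |
| 0.7 | 0.075 | 0.066 | 12% |

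**5. Interval half-widths by simulation** (20,000 trials per cell). Crude Welch is compared with ANCOVA using an HC3 (heteroscedasticity-robust) standard error and t with N − 3 degrees of freedom. Each cell shows Welch, then ANCOVA, then the shortening.

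| Setting | ρ = 0.3 | ρ = 0.5 | ρ = 0.7 |
|---|---|---|---|
| 24:12 | 0.859, 0.727 (15%) | 0.726, 0.659 (9%) | 0.561, 0.542 (3%) |
| 24:12, 10% set to baseline | 0.814, 0.706 (13%) | 0.688, 0.634 (8%) | 0.533, 0.519 (3%) |
| 24:12, 20% set to baseline | 0.765, 0.680 (11%) | 0.647, 0.607 (6%) | 0.501, 0.492 (2%) |
| 16:8 | 1.082, 0.936 (14%) | 0.916, 0.851 (7%) | 0.709, 0.703 (1%) |

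The 10% and 20% rows apply the SAP 2.6.3 replacement rule at assumed rates. The 16:8 row is an assumed oral subset: in the MLP cohort, REU is scored only in patients with oral disease (protocol 8.3.3, SAP 5.7.5), so its arms may be smaller than 24 and 12. At ρ = 0.8 the gain is under 1% at 24:12, and at 16:8 the HC3 interval is about 2% wider than Welch.

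**6. Why HC3.** If the placebo residual SD is 1.5 times that of the active arm (assumption), pooled-variance ANCOVA covers only 0.913 to 0.918. HC3 covered 0.951 to 0.963 across the cells examined.

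**The case against.** The other side has a good case. This is a small proof-of-concept trial whose decision rests on IGA alone. The secondary objective is to evaluate, not to demonstrate. SAP Table 2-1 sets Q4W beside placebo for every efficacy endpoint in Period 1, which is a descriptive comparison, and the protocol makes the same choice. All of this stands and keeps the point minor. It does not remove it, because the plan is not purely descriptive: it gives intervals against placebo for the binary endpoints and stops at the scores.

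A reader can also derive a crude interval, so no comparison is lost. That stands too. One might infer that only the sponsor could produce an adjusted interval. That goes too far: the ANCOVA estimate and its model-based standard error follow exactly from per-arm N, means and SDs of baseline, Week 16 score and change, since the three variances fix the covariance. Baseline summaries are planned, although on the randomized set; the SD of the Week 16 score on the same patients is not explicitly promised. Only the HC3 variant needs patient-level data.

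A reader might extend the point to the DLQI scores, itch, pain, OLPSSM and Scalpdex, which have the same wording in 2.6.1. The documents do not support that. SAP 2.11 refers to Section 2.6 and also to Section 2.13 "for the analysis method of Patient-reported outcomes", and 2.13 is not legible in the public copy. REU and LPPAI are not patient-reported and are not sent there, but other redacted text could still cover them.

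**Conclusion.** The point holds as a low-priority improvement for REU and LPPAI, within the readable text. The objective is comparative, and no readable passage plans a contrast for these two scores.

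A reader might infer that the secondary objective goes unserved, or that SAP and protocol conflict. Neither follows: the binary endpoints have planned differences, and the SAP matches protocol 12.5.1. The proof-of-concept rule and the 71% are unaffected.

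The benefit is one prespecified estimate per score and an interval shorter than crude Welch by about 15%, 9% or 3% at 24:12 (14%, 7% or 1% at 16:8) for correlations of 0.3, 0.5 or 0.7. It vanishes at about 0.8. These sizes rest on assumed correlations, equal SDs and, for 16:8, an assumed oral subset; none of these is given in the documents.

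**What to change.** In SAP 2.6.2, replace the present entry with this specification:

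- **Model:** ANCOVA of absolute change from baseline at Week 16 on treatment and baseline score.
- **Scores:** REU total in MLP-cohort patients with oral disease; LPPAI in the LPP cohort.
- **Data:** as they stand after the SAP 2.6.3 rule.
- **Report:** adjusted difference, Q4W minus placebo, with a 95% confidence interval (HC3 standard error, t with N − 3 degrees of freedom) and the number analysed per arm.
- **Label:** supportive, not adjusted for multiplicity.

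Keep other visits, percentage change and the patient-reported scores as planned.

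The cost is two extra intervals, with no new data or visits. The two cohorts contain different patients, so with no true effect the chance that at least one interval excludes zero is 1 − 0.95² = 9.75%. Extending the model to every patient-reported total would give 13 intervals: three cohorts each for DLQI, itch and pain (one question each), plus REU, OLPSSM, LPPAI and Scalpdex. That chance could then reach about 49% if they were independent (1 − 0.95¹³), a further reason to stop at two. The other drawbacks are a common linear baseline slope assumed for bounded scores, and slight conservatism of HC3 at these sizes.

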### **Oral Lichen Planus Symptom Severity Measure (OLPSSM)**

OLPSSM was a PRO-based assessment of the symptom experience of subjects with oral lichen planus in clinical studies, ranging from 0 to 28, with higher scores indicating worse severity.

Summary statistics will be provided for absolute and percentage change from baseline of OLPSSM score by visit up to end of study for each treatment group.

- Endpoints for LPP**

#### **LPP Activity Index (LPPAI)**

LPPAI is a numeric score to quantify the signs and symptoms of LPP (Chiang, 2010). Subjects with an LPPAI reduction greater than 85% over pretreatment values were considered responders, with 25% to 85% reduction were considered partial responders, and with less than 25% reduction were considered non-responders.

Summary statistics will be provided for absolute and percentage change from baseline of LPPAI score by visit up to the end of study for each treatment group.

The number and proportion of LPPAI responders and partial responders will be presented by visit up to the end of study for each treatment group.

#### **Scalpdex**

Scalpdex is a self-administered, health-related quality of life instrument originally developed for scalp dermatitis. This survey includes 23 items, each item scored on a scale of 0-100, where 0=never, 25=rarely, 50=sometimes, 75=often and 100=all the time. The 23 items are mapped into 3 major domains that affect patient quality of life: symptoms, functioning, and emotions. The Scalpdex will be evaluated both as a total score, calculated as the mean of all 23 items, and by 3 dimensions, calculated as the mean of the item scores pertaining to each domain (Chen, 2002).

Summary statistics will be provided for absolute and percentage change from baseline of Scalpdex total score and scores of 3 domains by visit up to end of study for each treatment group.

**Table 2-5 Overview of analysis methods for secondary efficacy variables**

Variable(s)	Cohorts applied	Summary statistics for discrete data	Statistical analyses	Summary statistics for continuous data	Graphs*
IGA response over time a	CLP, MLP, LPP	X	Fisher exact test @ Week 1- 16		X
DLQI 0/1 response over time	CLP, MLP, LPP	X			X
DLQI total score and item score overtime	CLP, MLP, LPP			X	X b
Patient Assessment of Itch (NRS) over time (3 questions)	CLP, MLP, LPP			X	
Patient Assessment of Pain (NRS) over time (3 questions)	CLP, MLP, LPP			X	
PSAD over time	CLP	X			X c
REU over time	MLP			X	X d
OLPSSM over time	MLP			X	
LPPAI responder and partial responder over time	LPP	X			
LPPAI score over time	LPP			X	X d
Scalpdex over time	LPP			X	

\*Line plots. The graphs may only be presented in the Rshiny app where appropriate.

aIGA responses include: 1) IGA ≥2 points improvement response and 2) IGA= 0 or 1 response.

bTotal DLQI score change from baseline by cohort.

cPlotted as a categorical variable.

dTime course of percent change from baseline.

## 2.6.2 Statistical hypothesis, model, and method of analysis

Not applicable

## 2.6.3 Handling of missing values/censoring/discontinuations

Data collected after treatment discontinuation by Week 32 will be replaced with the baseline value of the patients for all secondary endpoints above. Missing values not related to treatment discontinuation will be analyzed as observed.

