#### **Treatment Period 1: Week 0-16**

- Patients in the active **secukinumab 300 mg every 4 weeks treatment arm** receive induction with secukinumab 300 mg s.c. at Weeks 0, 1, 2, 3, 4 and then secukinumab 300 mg s.c. every 4 weeks, meaning at Weeks 8 and 12.
- Patients in the **placebo for 16 weeks followed by secukinumab 300 mg every 2 weeks treatment arm** receive corresponding placebo injections s.c. at Weeks 0, 1, 2, 3, 4 and then every 4 weeks, meaning at Weeks 8 and 12.

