## **9 Study discontinuation and completion**

### **9.1 Discontinuation**

#### **9.1.1 Discontinuation of study treatment**

Discontinuation of study treatment for a subject occurs when the study treatment is stopped earlier than the protocol planned duration (i.e., < Week 32) and can be initiated by either the subject or the investigator.

The investigator must discontinue study treatment for a given subject if he/she believes that continuation would negatively impact the subject's well-being. Prior to discontinuation this should be discussed with and communicated to the sponsor's medical expert.

Study treatment must be discontinued under the following circumstances:

- Subject decision
- Withdrawal of consent
- Pregnancy
- A patient on placebo treatment in Treatment Period 1 achieves spontaneous remission (defined by an IGA of 0 or 1) at the Week 16 visit
- Ongoing use of prohibited treatment, use of a prohibited treatment that results in an undue safety risk for the subject as per the investigator's clinical judgment, or receipt of a live virus vaccine during the study (as detailed in [Section 6.2.2](#))
- Any protocol deviation in which study participation might result in a safety risk to the subject
- Emergency unblinding
- AEs that in the judgment of the investigator/qualified site staff, taking into account the patient's overall status prevent the subject from continuing study treatment
- Any laboratory abnormalities that in the judgment of the investigator, taking into consideration the patient's overall status, prevents the subject from continuing participation in the study

If discontinuation of study treatment is due to the subject, the investigator should make a reasonable effort to understand the primary reason for the subject's premature discontinuation of study treatment and to record this information.

Subjects who discontinue study treatment should NOT be considered withdrawn from the study UNLESS they withdraw their consent (see [Section 9.1.3 'Withdrawal of Informed Consent'](#)).

Subjects should continue attending planned site visits and perform the study assessments until the last visit of the study period during which they discontinue (Week 16 or Week 32).

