#### **Treatment Period 1:**

Treatment Period 1 is placebo-controlled and covers the time from Week 0 (randomization visit) to Week 16. Patients who meet all eligibility criteria are randomized in a 2:1 ratio to one of the following two treatment arms **within** their cohort:

- **Secukinumab 300 mg every 4 weeks (Q4W) arm:** subjects receive a weekly induction treatment from baseline to Week 4 followed by secukinumab 300 mg every 4 weeks.

- **Placebo for 16 weeks followed by secukinumab 300 mg every 2 weeks (Q2W) arm:** subjects receive matching placebo injections.

Thirty-six patients will be randomized per cohort, 24 to active and 12 to placebo treatment, which means that the study will enroll approximately 108 subjects in total.

In Treatment Period 1 all subjects receive weekly subcutaneous injections of blinded study drug (either 300 mg secukinumab or placebo) at Weeks 0, 1, 2, 3 and 4. Thereafter the frequency of blinded study drug injections for all subjects is every 4 weeks up to Week 16. Home administration of study drug is **not** allowed during Treatment Period 1, except for the case of a pandemic. Subjects who complete Treatment Period 1 roll over to Treatment Period 2 at the Week 16 visit. The only exception are subjects from the placebo for 16 weeks followed by secukinumab 300 mg every 2 weeks arm, who achieve spontaneous remission at the Week 16 visit. Spontaneous remission is defined as an IGA of 0 or 1 at Week 16. These subjects do **not** proceed to Treatment Period 2 to avoid unnecessary treatment. Instead, they will directly enter the Follow-up Period after the Week 16 visit.

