### Follow-up:

There is an 8-week Follow-up Period after Week 32. The End of Study (EOS) is reached at Week 40. If a subject discontinues study during Follow-up period, visit Week 40 has to be performed.

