### **2.1.1.3 Day of last dose of study treatment**

The date of last dose will be collected via the CRF. The subject’s exposure will be calculated considering the end of study period visit (including follow-up visits F4, F8) or last dose day +84 days whichever occurs earlier.

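### SAP 2.6.3 does not exempt placebo patients stopped for remission at Week 16, so observed remission could appear as baseline severity in the Week 20 and Week 24 summaries

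*SAP*

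**What the plan says.** SAP 2.6.3 gives one rule for all secondary endpoints: "Data collected after treatment discontinuation by Week 32 will be replaced with the baseline value of the patients for all secondary endpoints above". Other missing values are analysed as observed. The SAP document history records that Amendment 3 widened this baseline replacement from Treatment Period 1 to the entire treatment period.

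Protocol 9.1.1 says that discontinuation of study treatment occurs when "study treatment is stopped earlier than the protocol planned duration", meaning before Week 32. Among the circumstances that require it is: "A patient on placebo treatment in Treatment Period 1 achieves spontaneous remission" at the Week 16 visit, defined as IGA 0 or 1.

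SAP 1.1 describes the same patients differently. Patients who complete Treatment Period 1 roll over to Treatment Period 2, and "The only exception are subjects from the placebo for 16 weeks followed by secukinumab 300 mg every 2 weeks arm" who are in remission at Week 16. It continues: "Instead, they will directly enter the Follow-up Period after the Week 16 visit".

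Two statements bear on when their follow-up visits take place. SAP 1.1 says "There is an 8-week Follow-up Period after Week 32", and Protocol Table 8-1 prints follow-up visits only at Week 36 (Day 253) and Week 40 (Day 281). SAP 2.1.1.3, in defining exposure, refers to the "end of study period visit (including follow-up visits F4, F8").

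For efficacy over the entire treatment period, SAP Table 2-1 lists three columns: secukinumab Q4W, placebo, and placebo to secukinumab Q2W. It does not say which one holds a placebo patient who never switched.

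**The concern.** Baseline replacement normally treats a stop as a failure. Here the stop is caused by success. A placebo patient taken off treatment because IGA fell to 0 or 1 could be shown at later visits with the severity that qualified the patient for entry. A secukinumab patient with the same Week 16 result continues treatment (Protocol 4.1) and keeps the observed values. The same clinical outcome would then be recorded in opposite ways in the two arms.

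The column question adds to this. Evaluating Q2W in Treatment Period 2 is a secondary objective. If never-switched patients are counted in the placebo-to-Q2W column, their values enter the results of a regimen they did not receive: downward if reset to baseline, upward if observed remission is kept. The visible estimand charter (SAP 5.4.1) says that it covers the primary endpoint, so it does not settle the matter.

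**Working it through.** The plan gives no figure for this point. Its 71% probability of a positive result per cohort (SAP Section 3) was recalculated by exact enumeration of both binomials with Beta(1/3, 1/3) priors. The result is 0.712, as in SAP Table 3-1. It uses only the Week 16 primary response and is not affected here.

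**1. Does the rule apply?** By Protocol 9.1.1, a remission stop is a discontinuation before Week 32. SAP 2.6.3 acts on treatment discontinuation and names no exception. Read together, the rule applies.

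**2. Which visits are reached?** Week 16 is Day 113 (SAP Table 2-3).
- Visits counted from Week 16: 113 + 28 = Day 141, in the Week 20 window (Days 128-155); 113 + 56 = Day 169, in the Week 24 window (Days 156-183). Both precede Week 32 (Day 225), so the values are replaced.
- Visits as printed: Days 253 and 281, in the Week 36 and Week 40 windows (Days 240-267 and 268-295). Both follow Week 32, so nothing is replaced.

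**3. What does replacement do?** Inclusion criterion 3 requires IGA of at least 3 at baseline. A replaced value is therefore IGA 3 or 4: non-response on both secondary IGA endpoints, and zero change on the continuous scores.

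**4. How many patients?** The placebo rate of IGA 0/1 is not in the documents. Assumed range: q = 2% to 20%. The upper end is the planning rate for IGA ≤2, of which IGA 0/1 is a subset. Expected number = nq; chance of at least one = 1 − (1 − q)^n.

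| q | Expected of 12 | Expected of 36 | At least one of 12 | At least one of 36 |
|---|---|---|---|---|
| 2% | 0.24 | 0.72 | 21.5% | 51.7% |
| 5% | 0.6 | 1.8 | 46.0% | 84.2% |
| 10% | 1.2 | 3.6 | 71.8% | 97.7% |
| 20% | 2.4 | 7.2 | 93.1% | >99% |

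**5. What if they are counted in the placebo-to-Q2W column?** Let p be the response rate in switched patients (an assumption) and r the number in remission among 12. The column shows p(12 − r)/12 if they are reset, [p(12 − r) + r]/12 if observed remission is kept, and p if they are left out. At p = 50%:

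| r | Reset to baseline | Observed kept | Left out |
|---|---|---|---|
| 1 | 45.8% | 54.2% | 50.0% |
| 2 | 41.7% | 58.3% | 50.0% |

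For r = 1 the drop from leaving out to resetting is p/12: 2.5, 4.2 and 5.0 points at p = 30%, 50% and 60%. The standard error √(p(1 − p)/12) is 13.2, 14.4 and 14.1 points.

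**The case against.** The best defence is that the SAP does not class these patients as premature discontinuations. SAP 1.1 names them as an exception among patients who complete Treatment Period 1, and deals separately with those who stop early and attend an end-of-treatment visit. The only printed follow-up visits are Weeks 36 and 40, and the F4 and F8 labels occur in an exposure definition. This stands to the extent that the overwrite is conditional. It does not remove the problem: the protocol definition includes the stop, SAP 2.6.3 does not exclude it, and direct entry to Follow-up after Week 16 is more naturally read as visits 4 and 8 weeks later.

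The column point is also open to reply. The FAS analyses patients by assigned treatment, and the assigned arm is placebo followed by Q2W, so placement there is defensible. The placebo column may instead simply hold Treatment Period 1 placebo data. What remains is that membership is undefined.

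A reader might infer more than the documents support:
- *That Week 16 values are reset.* Placebo patients receive injections "receive corresponding placebo injections s.c. at Weeks 0, 1, 2, 3, 4 and then every 4 weeks, meaning at Weeks 8 and 12", so dating the stop by last dose would place it before Week 16. But Protocol 9.1.1 ties the stop to remission at the Week 16 visit, and Week 12 is the last Period 1 injection in both arms.
- *That Week 32 is filled in with baseline.* The document history uses the label BOCF, but the operative sentence replaces data that were collected. On neither timing do these patients have a scheduled Week 32 assessment.
- *That Weeks 36 and 40 are reset*, by attaching the Week 32 limit to the discontinuation instead of the data. The document history gives the scope as the treatment period.

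**Conclusion.** The point holds in a limited form and is minor. As written, the two documents together permit observed remission on placebo to be shown as moderate or severe disease, while remission on secukinumab is kept. This happens only if the remission stop counts as a discontinuation under SAP 2.6.3 and the follow-up visits are counted from Week 16. On the literal wording, the effect is then confined to descriptive Week 20 and Week 24 summaries. About 0.2 to 2.4 patients per 12 would be involved, at an assumed remission rate of 2% to 20%. Even if they were counted under Q2W, one reset patient moves a cohort's rate by 2.5 to 5.0 points for assumed p of 30% to 60%, well inside one standard error.

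The primary endpoint, the proof-of-concept criteria, the Week 1 to 16 Fisher tests and the named Week 16 and Week 32 endpoints are not affected. The documents do not support a claim that the trial's conclusions, or the Q2W results at Week 32, are biased. Parts of the SAP are redacted, so an exemption there cannot be excluded.

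**What to change.** 1. In SAP 2.6.3, state that the protocol-mandated Week 16 remission stop in the placebo arm is not a treatment discontinuation for baseline replacement, and that these patients' later data are analysed as observed.
2. In SAP Table 2-1, add a footnote defining which entire-period efficacy column holds placebo patients who never received secukinumab, so that their values, reset or observed, are not counted as results of the Q2W regimen. Label the Q2W summary as patients who switched.

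The cost is one sentence and one footnote, with no new data and no effect on the primary analysis. The drawback is that the Q2W summary no longer represents the full randomised arm, which the label must make clear. Any placebo entry after Week 16 would be a very small, selected group and should not be read as a comparator. No change to the remission rule itself is proposed.
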